7. RISK ASSESSMENT

7.1. Potential Risks from Peripheral Catheterization, Stenting and PTA

It is expected that risks associated with this study will be not significantly different than those with standard interventional procedures for PAD disease in the superficial or popliteal (P1 segment) arteries. The list of adverse events that may result from peripheral intervention includes but is not limited to: abrupt closure, acute myocardial infarction, allergic reaction to contrast, amputation, aneurysm, arrhythmias, arterial dissection/perforation/rupture, artery spasm, AV fistula, bleeding, bypass graft surgery, chest pain, death, discomfort during procedure, embolism (air, tissue, thrombosis, device), endocarditis, fever, groin bruising/discomfort, hematoma, hemorrhage, hypertension, hypotension, injury to groin vessel, infection or pain at insertion site, ischemia, nausea, pseudoaneurysm, renal failure, restenosis, sepsis/infection, stroke/CVA, wound complication/infection, total occlusion, vomiting/nausea.

7.2. Potential Risks from Everolimus Coating

Confidential Page 37 of 79

The oral formulation of everolimus has been evaluated in clinical investigations and has been approved in more than 90 countries. Everolimus has been approved for more than a decade and used as an immunosuppressant to prevent rejection of organ transplants and in the treatment of a number of cancers. Everolimus marketed under the trade names Zortress (USA), Certican (European Union and other countries) in transplantation medicine, and as Afinitor and Votubia in oncology⁴,⁵.

In animal studies, everolimus has shown a low acute toxic potential. No lethality or severe toxicity were observed in either mice or rats given single oral doses of 2000 mg/kg (limit test). In humans the toxicity data is limited; single doses of up to 70 mg have been administered with no difference in acute toxicity profile of what was observed for the 10 mg dose.

Everolimus is often used in combination with cyclosporine (microemulsion formulation) and corticosteroids.

Subjects treated with everolimus usually receive doses ranging up to 10mg/day over several months period and extending up to a year or more with achievement of state concentration within 4 to 7 days.

The following adverse events were noted in everolimus clinical investigations:

Abdominal pain, anemia, angioedema, anorexia, asthenia, constipation, cough, delayed wound healing/fluid accumulation, diarrhea, dyslipidemia, dyspnea, dysgeusia, dyspepsia, dysuria, dry skin, edema (peripheral), epistaxis, fatigue, headache, hematuria, hyperglycemia, hyperkalemia, hypertension, hypokalemia, hypomagnesaemia, hypophosphatemia, increased serum creatinine, infections, insomnia, interaction with strong inhibitors/inducers of CYP3A4 or PgP, leukopenia, male infertility, mucosal inflammation, nausea, neutropenia, non-infectious pneumonitis, pain, proteinuria, pruritus, pyrexia, rash, stomatitis, thrombocytopenia, thrombotic microangiography, thrombotic thrombocytopenic purpura, tremor, urinary tract infection, upper respiratory tract infection and vomiting⁶.

Certain side effects and discomforts have been reported in subjects that have received everolimus in intravenous (IV) form as part of chemotherapy treatment. These subjects may have other comorbid conditions and/or have received concomitant medications that may also have contributed to the reported side effects. In the IV setting, the dose is delivered throughout the body and in doses hundreds of times higher than the total amount present on the CVT Everolimus-coated PTA Catheter used in this clinical study. The side effects reported by the chemotherapy subjects include allergic/immunologic reactions, alopecia, anemia, blood product transfusion, gastro-intestinal symptoms, hematologic dyscrasia (including leukopenia, neutropenia, thrombocytopenia), hepatic enzyme changes, histologic changes in vessel wall, cellular damage or necrosis, myalgia/arthralgia and peripheral neuropathy.

Confidential Page 38 of 79

⁴ Trimukhe R, Vani P, Patel A, Salgotra V. Safety and performance of the EverProTM everolimus-eluting coronary stent system with biodegradable polymer in a real-world scenario. World J Cardiol. 2020;12(12):615-625. doi:10.4330/wjc.v12.i12.615

⁵ Meng, M., Gao, B., Wang, X. et al. Long-term clinical outcomes of everolimus-eluting stent versus paclitaxel-eluting stent in patients undergoing percutaneous coronary interventions: a meta-analysis. BMC Cardiovasc Disord 16, 34 (2016).

⁶ Certican® (Everolimus) Product Insert. Novartis, Mar 2013.

Based on current information available to date on everolimus as a drug entity and on the CVT Everolimus-coated PTA Catheter evaluated in preclinical studies, it is unlikely, with the total dosage on the CVT Everolimus-coated PTA Catheter and the targeted vessel delivery of the everolimus, that the side effects associated with high dose of everolimus would occur.

7.3. Risk Management Procedure

The CVT-SFA Trial will be conducted by skilled and trained investigators relative to interventional procedures and this protocol. The research team at each clinical site will undergo specific in-servicing and training prior to initiation of the study.

Subjects will be monitored closely throughout the study duration. Subjects will be evaluated clinically at pre-determined time points to assess their clinical condition. The subject's medication regimen will be in accordance with standard of care requirements for peripheral interventional procedures.

7.4. Potential Benefits

Given that paclitaxel, the drug used on most drug-coated balloons (DCBs) that have been a first-line treatment option of obstructive SFA disease since the mid-2010s, has a potentially increasing risk of late mortality at 2 years and beyond compared to patients treated with uncoated devices, ¹⁰¹ the replacement of paclitaxel with everolimus, a drug with a proven safety profile in drug-eluting stents (DES) and considered as the percutaneous treatment of choice for coronary artery disease (CAD), may be the alternative to reduce restenosis and late lumen loss in the superficial femoral and proximal popliteal arteries.

8. DATA HANDLING, RECORD KEEPING AND REPORTING

8.1. Case Report Form (CRF) Completion

All required study data will be accurately recorded by authorized personnel on CRFs which will be provided by CVT.

8.2. Source Documentation

Regulations require that investigators maintain information in the subject's medical records, which corroborate data collected on the CRFs. Investigators will maintain all records pertaining to this study as mandated by the hospital requirements and national laws and regulations.

8.3. Reports

A report will be created after the primary endpoints have been analyzed and a final report on the study will be completed at the end of the study. Interim reports may be compiled, at the request of the sponsor, for regulatory purposes.

9. REGULATORY REQUIREMENTS

9.1. Investigator's Responsibility

Prior to enrolling subjects for this study, the investigator must read and understand the

Confidential Page 39 of 79

protocol and must sign and complete an investigator agreement form. The investigator agreement form documents the investigator's agreement to all conditions of the protocol and an agreement to conduct the study accordingly.

This study will be conducted in accordance with Good Clinical Practice (GCP), ISO14155:2020 and the Declaration of Helsinki as well as any local or regional regulations.

Additional requirements must be met by the investigator and participating institutions.

9.2. Compliance with Protocol and Protocol Amendments

A protocol deviation is defined as any change, divergence or departure from the study design or procedures of a research protocol that is under the investigator's control and that has not been approved by the IRB/EC. The investigator is responsible for promptly reporting protocol deviations to their IRB/EC per IRB/EC policy and to the sponsor. The sponsor will determine the effect of the protocol deviation on the scientific soundness of the clinical study and subject safety and determine if additional reports or actions are required. Additional action may include site re-training, removal of the devices, and/or site termination.

The investigator will not implement any changes to the protocol without first obtaining in written agreement from the sponsor and documented approval from the EC, except in the event of an immediate hazard to the subject. The investigator will report the deviation in accordance with the applicable regulations.

9.3. Investigator Requirements

All investigators must submit the following documentation to be considered approved investigators. The Sponsor will make final determination of approved investigators.

- Signed investigator's agreement
- Completed site specific in-servicing and training

Investigators must allow CVT or representatives of CVT to visit the site to periodically assess the data quality and study integrity. On site, CVT, or its representatives, will review study records in comparison with source documents, discuss the conduct of the study and verify that the facilities remain acceptable. In addition, the study may be evaluated by government inspectors who must be allowed access to CRFs, source documents and other study files.

The investigator must notify CVT promptly of any inspections scheduled by regulatory authorities and promptly forward copies of inspection reports to CVT.

The investigator should retain essential documents at least two years after the last approval of a marketing application and until there are no pending or contemplated marketing applications, or at least two years have elapsed since the formal discontinuation of clinical development of the investigational product. These documents should be retained for a longer period, however, if required by the applicable regulatory requirements or by an agreement with the sponsor. It is the responsibility of the sponsor

Confidential Page 40 of 79

to inform the investigator/institution as to when these documents no longer need to be retained.

9.4. Institutional Requirements

The investigator and institution are required to submit the following documentation prior to shipment of first device and first treatment procedure:

- IRB/EC approved informed consent form
- IRB/EC approval of the final protocol

Any additional requirements imposed by the IRB/EC or regulatory authorities concerning the trial shall be followed.

9.5. Informed Subject Consent

If it is mandated by the respective country regulations, study subjects must provide written informed consent using an IRB/EC-approved informed consent form. The study must be explained to the study subjects in lay language. The investigator, or representative, must be available to answer all subjects' questions. Subjects will be assured that they may withdraw from the study at any time for any reason and receive alternative conventional therapy as indicated.

9.6. Device Accountability

This trial is a first-in-human study and devices may not be used for the treatment of subjects not qualified for inclusion into the study. The Investigator will maintain adequate records of the receipt and disposition of the investigational device, including lot numbers, device identification number, date used, subject ID number and treating physician. A device accountability log supplied by the Sponsor will be used.

Use of any investigational device outside of the protocol is strictly forbidden and may constitute grounds for removal of the investigator/site from the clinical trial/investigation.

9.7. Use of Information and Publication

All information and data generated in association with this study will be held in strict confidence until the study completion. The investigator agrees to use this information for the sole purpose of completing this study and for no other purpose without written consent from sponsor.

At the conclusion of each follow-up time point and the entire study, an abstract reporting the primary results may prepared and presented in an appropriate international forum. A manuscript may also be prepared for publication in a scientific journal. The data and results from the study are the sole property of CVT. CVT shall have the right to access and use all data and results generated during the study. CVT acknowledges that the Principal Investigator(s) might desire to publish a multi-center publication regarding the trial results. CVT must receive any proposed publication and/or presentation materials at least 60 days prior to the proposed date of the presentation or the initial submission of the proposed publication in order for the materials to be

Confidential Page 41 of 79

reviewed by CVT in compliance with CVT publication policy set forth in the Research Agreement or Investigator's Agreement.

9.8. Reporting Requirements

The investigator should notify the IRB/EC in writing within three months after completion, termination, or discontinuation of the study at the site. The same procedure will be applied to Competent Authority where required. A site reporting requirements summary is presented in **Table 3**.

Table 3. CVT-SFA Study Site Responsibilities for Submitting Data and Reports

Type of CRF/Report	Time Frame	Process
CRF (baseline, in-hospital summary, follow-up, non-compliance, reconciliation form, subject withdrawal)	Ongoing basis	CRF
Adverse Events	Ongoing Basis	CRF Details to be retrieved at monitoring visit
Serious Adverse Event Notification CRF (including death, device malfunction; failure, near incident, unanticipated adverse device effects)	Within 24 hours	Input within 24 hours of knowledge of event
Annual reports	Annually, as required by Ethic Committee	Material to be prepared by sponsor and copy to be provided to EC by investigator
Final report	Within 6 months of study completion or termination	Material to be prepared by sponsor and copy to be provided to EC by investigator

10. SPONSOR RESPONSIBILITIES COMPLIANCE/QUALITY ASSURANCE

10.1. Role of Sponsor

As the study sponsor, CVT has the overall responsibility for the conduct of the study, including assurance that the study satisfies international standards and the regulatory requirements of the relevant Competent Authorities.

General Duties

It is the sponsor's responsibility to ensure that the study is conducted according to Good Clinical Practice (GCP), ISO 14155:2020, the Declaration of Helsinki, and other applicable

Confidential Page 42 of 79

regulatory requirements, the study protocol, or any conditions of approval imposed by the IRB/EC or regulatory authorities. Additionally, the sponsor will ensure proper clinical site monitoring is conducted.

Selection of Clinical Investigators and Sites

The sponsor will select qualified investigators and facilities which have adequate study subject population to meet the requirements of the investigation.

Training of Investigator/Site Personnel and Periodic Monitoring

The training of the investigator and appropriate clinical site personnel will be the responsibility of the sponsor and PI, or designee, and may be conducted during an investigator meeting, a site initiation visit or other appropriate training sessions.

Periodic monitoring visits will be conducted frequently enough to ensure that all clinical subject data are properly documented and that the study is properly conducted.

10.2. Investigator's Brochure

The sponsor will prepare, assemble and maintain all pre-clinical and available clinical data and documentation and will summarize this information in the clinical investigator's brochure.

10.3. Documentation

The sponsor will collect, store, guard and ensure completion by the relevant parties of the following documents:

- Records of any serious adverse events (SAEs) reported to the sponsor during the clinical investigation
- Any statistical analyses and underlying supporting data
- The final report of the clinical investigation

10.4. Committees

Clinical Events Committee

The Clinical Events Committee (CEC) is made up of angiologists/radiologists/cardiologists or vascular surgeons who are not participants in the study. The CEC is charged with the development of specific criteria used for the categorization of clinical events and clinical endpoints in the study which are based on the protocol.

At the onset of the trial, the CEC will establish explicit rules outlining the minimum amount of data required and the algorithm to be followed in order to classify a clinical event. All members of the CEC will be blinded to the primary results of the trial.

The CEC will meet regularly to review and adjudicate all clinical events in which the required minimum data is not available. The committee will also review and rule on all deaths that occur throughout the trial.

Confidential Page 43 of 79

Steering Committee

The steering committee (SC) is the main policy and decision-making committee of the study and has final responsibility for the scientific conduct. The specific tasks of the SC are to:

- Proper design and conduct of the trial
- Ethical and professional standards of the trial
- Ensuring that the results of the clinical trial and the scientific accomplishments are arrived at in the most efficient manner possible
- Periodical safety review
- Publication policy

The steering committee will be composed of the lead principal investigator, at least one investigator of a clinic participating in the trial and representatives from CVT.

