3. STUDY DESIGN

The CVT-SFA Trial investigates the inhibition of restenosis using the CVT Everolimus-coated PTA Catheter in the treatment of de-novo occluded/ stenotic or re-occluded/ restenotic superficial femoral or popliteal arteries. The clinical study will be a prospective, multi-center, open, single-arm study.

Each subject will be followed for at least 3 years (36 months) after treatment. All subjects will have a follow-up contact or an optional office/hospital/clinic visit at 30 days. A follow-up office/hospital/clinic visit will occur at 6 and 12 months and a follow up phone call will occur at 24 and 36 months.

To participate in this study, the site will need the resources necessary for conventional vascular surgery as well as for fluoroscopy-guided catheter-based procedures with high quality imaging.

The study participation flow chart is provided in Figure 1.

[figure not shown]

Figure 1. CVT-SFA Study Participation Flow Chart

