5.6. Procedures for Reporting Serious Adverse Event

Criteria for Reporting Serious Adverse Event

Serious adverse events are required to be reported for the following situations:

- a. Any serious adverse event that has a causal relationship with the investigational device or the investigation procedure or where such as causal relationship is reasonably possible.
- b. Any device deficiency that might have led to a serious adverse event if appropriate action had not been taken, intervention had not occurred or circumstances had been less fortunate.
- c. Any new findings in relation to any event referred to in points (a) and (b) above.

Reporting by the Sponsor to National Competent Authorities

The Sponsor must report serious adverse events to the National Competent Authorities (NCAs) where the clinical investigation has commenced per the following timelines:

- For all reportable events which indicate an imminent risk of death, serious injury or serious illness and that requires prompt remedial action for other subjects, users or other persons or a new finding to the event: *Immediately but not later than two (2) calendar days after awareness by the Sponsor of a new reportable event or of new information in relation with an already reported event.*
- For other reportable events or a new finding/update: *Immediately but not later* than seven (7) calendar days following the date of awareness by the sponsor of

Confidential Page 33 of 79

the new reportable event or of new information in relation with an already report event.

Reporting by the Clinical Trial Investigator to the Sponsor

The Clinical Trial Investigator will report to the Sponsor immediately but no later than three (3) calendar days after investigational site study personnel become aware of the event.

Risk Assessment

In conjunction with the Coordinating Clinical Investigator and/or, if need be, the Clinical Event Committee (section 10.4), the Sponsor shall decide whether, as a result of a serious adverse event, the safety of study participants is at risk or whether continuation of the trial is in jeopardy.

Corrective Measures

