A revascularization of the target lesion is considered clinically-indicated if angiography shows a percent diameter stenosis $\geq 50\%$ and there is worsening of the Rutherford Becker Clinical Category that is clearly referable to the target lesion. (worsening is defined as a deterioration (an increase) in the Rutherford Becker Clinical Category by more than 2 categories from the earliest post-procedural measurement or to a category 5 or 6.) An independent angiographic core laboratory should verify that the severity of percent diameter stenosis meets requirements for clinical indication and will overrule in cases where investigator reports are not in agreement.

Target Extremity Revascularization (TER)

Target extremity revascularization (TER) is defined as any percutaneous intervention or surgical bypass of any segment of the target extremity. The target extremity is defined as the ipsilateral limb arteries proximal and distal to the target lesion, which includes upstream and downstream branches and excludes the target lesion itself.

Serious Adverse Event (SAE)

An Adverse Event is considered serious if the event led, or might have led, to one of the following outcomes:

- Death of a subject
- Serious deterioration in the health of a subject that resulted in any of the following:
 - Life-threatening illness or injury
 - o Permanent impairment of a body structure or body function
 - o Hospitalization or prolongation of patient hospitalization
 - Medical or surgical intervention to prevent life-threatening illness or injury or permanent impairment to a body structure or body function
 - Chronic disease
- Foetal distress, foetal death or a congenital physical or mental impairment or birth defect

Note: Planned hospitalizations for pre-existing conditions or a procedure required by this protocol without serious deterioration in health is not considered a serious adverse event.

Successful Pre-Dilatation

Pre-dilatation has been successfully completed without complications if all of the following apply:

- Diameter stenosis $\leq 70\%$ (by visual estimate)
- Lesion length still within the requirements of the protocol/CIP
- No angiographic complications

Superficial Femoral Artery (SFA)

Confidential Page 60 of 79

The SFA connects to the popliteal artery at the opening of adductor magnus or hunter's canal towards the end of the femur.

Thrombosis

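### Section 10.4 does not assign fully documented non-fatal MAE components to the events committee, leaving amputations and the symptom half of TLR without independent classification

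*Combined protocol and SAP*

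**What the plan says.** Section 10.4 sets up a Clinical Events Committee (CEC) of "angiologists/radiologists/cardiologists or vascular surgeons who are not participants in the study". It has a rule-setting task: when the study begins, it fixes how much data a case needs and the algorithm by which the case is classified. It then has two case-review tasks. The first is "The CEC will meet regularly to review and adjudicate all clinical events in which the required minimum data is not available". The second is "The committee will also review and rule on all deaths that occur throughout the trial". The only other mention of a CEC task is in section 5.6, where the sponsor judges the consequences of a serious adverse event: "In conjunction with the Coordinating Clinical Investigator and/or, if need be, the Clinical Event Committee (section 10.4").

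Section 3.1 defines MAE as cardiovascular death, index-limb amputation or ischemia-driven TLR. Ischemia-driven TLR is also part of patency. Appendix B defines clinically indicated TLR by two criteria: angiographic stenosis of at least 50%, and Rutherford worsening attributable to the target lesion. On the first it says "An independent angiographic core laboratory should verify that the severity of percent diameter stenosis meets requirements for clinical indication" and that the laboratory "will overrule in cases where investigator reports are not in agreement". It names no independent assessor for the second.

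On design, section 3 says "The clinical study will be a prospective, multi-center, open, single-arm study".

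**The concern.** An events committee normally classifies every potential endpoint event. Here the referral rule points the other way: the non-fatal events named for review are those that fall short of the minimum data. The separate sentence on deaths supports the literal reading, since it would not be needed if all endpoint events went to the committee. If the wording is a drafting slip, no other section corrects it, and the committee would still work from it.

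With one arm and a fixed OPC, classification error cannot cancel between groups. An MAE that is not counted raises the observed freedom from MAE directly. The MAE rate is also the early-stopping trigger in section 3.9, which is watched by the sponsor and a Steering Committee made up of investigators and sponsor representatives.

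**Working it through.** **Who checks what.** Setting sections 3.1, 10.4 and Appendix B side by side for events with complete data:

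| Component | CEC | Other independent check |
|---|---|---|
| Death | Yes, all | – |
| Index-limb amputation | Not assigned | None named |
| TLR: stenosis criterion | Not assigned | Angiographic core laboratory, with power to overrule |
| TLR: Rutherford worsening and attribution | Not assigned | None named |

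Two further points follow from the text.

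- The core-laboratory check is attached to *clinically indicated* TLR. MAE (section 3.1 and Appendix B) uses *ischemia-driven* TLR, which is not defined separately.
- Under section 3.1, restenosis is a PSVR above 2.4 read by the DUS core laboratory, or stenosis above 50% read by the angiographic core laboratory where an angiogram exists. A TLR that a site judges not to be ischemia-driven is therefore still a patency failure once either laboratory reads restenosis, whatever the symptoms. MAE has no such backstop.

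**Scale for the safety endpoint.** Inputs: N = 75, OPC 70%, assumed rate 70% + 15 points = 85%, one-sided alpha 0.025 and the 11-MAE example (section 6.3); Clopper-Pearson intervals (section 6.4).

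With x subjects free of MAE out of n, the limits are beta quantiles:

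- lower = Beta quantile at 0.025 with parameters (x, n − x + 1)
- upper = Beta quantile at 0.975 with parameters (x + 1, n − x)

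The plan's own figures come first. For 11 MAEs, x = 75 − 11 = 64, and the interval is 75.3% to 92.4%, as stated. The smallest x whose exact one-sided p-value against 70% is at most 0.025 is 61 (exact alpha 0.0187). The chance of at least 61 of 75 at a true rate of 85% is 85.3%, against 85% stated. Both reproduce.

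Moving the count, with p = P(X ≥ x) for X ~ Binomial(75, 0.70):

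| MAEs | Free of MAE | Lower 95% limit | One-sided p vs 70% |
|---|---|---|---|
| 11 | 64/75 = 85.3% | 75.3% | 0.002 |
| 14 | 61/75 = 81.3% | 70.7% | 0.019 |
| 15 | 60/75 = 80.0% | 69.2% | 0.035 |
| 17 | 58/75 = 77.3% | 66.2% | 0.102 |
| 18 | 57/75 = 76.0% | 64.7% | 0.157 |

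The lower limit crosses the OPC between 14 and 15 MAEs. To observe 11 when the correct count is 15, 4 of 15 (27%) would have to be missed.

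**Illustration of under-counting.** The fractions f below are assumptions; the documents give none. Take a true freedom from MAE of exactly 70%, so a true MAE rate of 30%. The apparent freedom from MAE is 1 − 0.30 × (1 − f), and the chance that the lower limit exceeds 70% is P(X ≥ 61) at that rate.

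| f | Apparent rate | Chance lower limit exceeds 70% |
|---|---|---|
| 0% | 70.0% | 1.9% |
| 5% | 71.5% | 3.5% |
| 10% | 73.0% | 6.4% |
| 20% | 76.0% | 17.3% |

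**The case against.** Several stronger readings are tempting, and the documents do not support them.

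- *Documented TLRs escape independent review.* They do not. The core laboratory verifies stenosis and can overrule the site, and Appendix M requires angiograms for clinical events to follow its guidelines. Only the symptom and attribution criterion is left.
- *Both primary endpoints are equally exposed.* They are not. The restenosis rule in section 3.1 catches most TLRs for patency, since a clinically indicated TLR itself requires at least 50% stenosis.
- *Investigators will classify most primary events themselves.* The plan does not say so. The CEC writes the criteria and the algorithm; who applies them to complete events is unstated. This is a gap in assignment, not a stated decision to leave classification to the sites.
- *Fourteen MAEs is the boundary for success.* The plan sets no such boundary. Sections 6.1 and 6.3 say significance is neither necessary nor sufficient, and section 6.1 gives a trend of p ≤ 0.15 as an example of what may justify further work. At 15 MAEs (p = 0.035), and even at 17 (p = 0.102), that example is still met.

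It is also fair to say that CEC members in a single-arm trial know the treatment too, so they add independence rather than blinding. Whether an amputation took place is largely a matter of fact, so review adds less there than for TLR. These points narrow the concern but do not remove it: the feasibility framing makes the estimated MAE rate the focus, and misclassification biases an estimate as readily as a test.

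**Conclusion.** The concern holds in a limited form. Read literally, section 10.4 gives the CEC incomplete events and deaths, and no other section assigns it fully documented non-fatal MAE components or says who applies its algorithm to them. Independent classification is missing for index-limb amputation and for the Rutherford and attribution half of TLR. It is present for deaths and for stenosis. The exposure is chiefly to the primary safety endpoint and its estimated MAE rate.

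The size cannot be fixed from the documents. Four events separate the plan's 11-MAE example from the first count at which the exact lower limit falls below the 70% OPC. That distance is a sense of scale, not a predicted error, and the under-count fractions are illustrative. The conclusion assumes that section 10.4 is followed as worded and that no separate committee charter, which the documents do not include, widens the remit.

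**What to change.** Replace the referral sentence in section 10.4 with: *The CEC will review and adjudicate all deaths, all index-limb amputations and all target lesion revascularizations, whether or not they are reported as ischemia-driven and whether or not the minimum data are complete, together with every other clinical event that falls short of the minimum data.*

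Including every TLR matters because a TLR wrongly reported as not ischemia-driven would otherwise never be seen. The last clause keeps the present cover for poorly documented thrombosis, embolic and access-site events, which are secondary endpoints.

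Also state whether ischemia-driven TLR (section 3.1 and the MAE definition in Appendix B) is the same as clinically indicated TLR (Appendix B), or define each, so that the committee applies one criterion.

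The cost is a short text change and a small number of extra dossiers for a committee that already exists. Sample size, visits and treatment are unaffected.
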